4.3 Definition of Baseline

Baseline measurement is defined as the latest measurement prior to first dose of each IMP (for WBA will this be defined as 24h pre-dose).

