9. Clinical chemistry only on Day 2 and Day 6. Approximately 8 h post-dose on Day 2 and pre-dose on Day 6. No clinical laboratory sampling on Day 4, 5, 7 and 8.
10. Blood pressure and pulse, see Section 11.3.3.
11. For timing of assessments, refer to Table 8.1-4.
12. Once daily administration of IMP. On Day 1 and Day 10, administration under fasting conditions, i.e. fasting for 10 h before IMP administration until 4 h post administration. On Days 2 to 9, administration prior to breakfast at the same time each morning (±1 h).
13. Includes sampling for future exploratory analyses of potential GS-248 metabolites.
14. Pre-dose PK samples on Day 8, 9 and 10 must be taken within 5 minutes before dose.
15. Future exploratory analyses of biomarkers e.g. inflammatory biomarkers.
16. Urine for analysis of AA metabolites and for future analysis of GS-248 metabolites and biomarkers will be collected at the following intervals: 0 to 6 h, 6 to 12 h and 12-24 h post administration of study drug on Day 1 and Day 10. In addition, baseline urine is collected -24 h to -12 h and -12 h to 0 h prior to the first IMP administration on Day -1/Day 1.
17. Breakfast, lunch, snack, dinner and evening snack. Standardised meals during 24 h after dose on Day 1 and Day 10. For timing of meals, refer to Table 8.1-4. No breakfast on Day 1 and Day 10. Breakfast only on Day 3 and Day 12.
18. From administration of IMP.

Table 8.1-4 Detailed schedule of events for Visit 2 and Visit 8, Part II (MAD)

| Assessment/time-point | Day -1 | Day 9 | Day 1/Day 10 | | | | | | | | | | | Day 2/Day 11 | | Day 3/Day 12 |
|--|-----------------|-----------------|--------------------|-------|------|----|----|----|--------------------|----|-----|-----|-----------------|-----------------|-----------------|--------------|
| | Admission | Pre-dose | 0 | 0.25h | 0.5h | 1h | 2h | 4h | 6h | 8h | 12h | 16h | 24h | 36h | 48 h | |
| Inclusion/exclusion criteria | | | X ¹ | | | | | | | | | | | | | |
| Pregnancy test (WOCBP) | X | X | | | | | | | | | | | | | | |
| Urine drug screen | X | X | | | | | | | | | | | | | | |
| Alcohol breath test | X | X | | | | | | | | | | | | | | |
| Physical examination | | | X ^{1,2} | | | | | | | | | | | | X ³ | |
| Clinical laboratory profile | X | X | | | | | | | | | | | X ⁵ | | X | |
| Vital signs ⁶ | X | X | X | | | | X | X | X | X | X | X | X | X | X | |
| Body temperature | | | X ⁴ | | | | | | | | | | | | | |
| 12-lead ECG | | | X ⁴ | | | | | X | | | X | | X ⁷ | | X | |

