| Randomisation | | | X ⁸ | | | | | | | | | | | | | |
| IMP administration | | X | | X | | | | | | | | | X ⁹ | | X ⁹ | |
| PK blood sampling | | X ¹¹ | X ^{10,11} | | X | X | X | X | X | X | X | X | X | X ¹² | X ¹³ | |
| Blood sampling for GS-248 MIST ¹⁴ | | | X ¹¹ | | X | X | X | X | X | X | X | X | X ¹² | | | |
| Blood sampling for WBA | | | X ¹⁰ | | | | | X | | | X | | X | | | |
| Blood sampling for ADMA analysis | | | X ¹⁰ | | | | | X | | | X | | X | | | |
| Blood sampling for future biomarker analyses | | | X ¹⁰ | | | | | X | | | X | | X | | | |
| Urine collection ¹⁵ | X | | | | | | | X | | | X | | X | | | |
| Breakfast ¹⁶ | | X | | | | | | | | | | | X | | X | |
| Meals | X ¹⁷ | X ¹⁷ | | | | | | | X ^{17,18} | | | | X ¹⁷ | | X ¹⁷ | |
| Baseline symptoms | X | | X | | | | | | | | | | | | | |
| AEs and SAEs | | | | | | | | | | | X | | | | | |
| Prior and concomitant medications | | | | | | | | | X | | | | | | | |

1. Day -1 or pre-dose Day 1 prior to randomisation. Not Day 10.
2. Short version of physical examination.
3. Physical examination Day 12, not Day 3.
4. Day -1/Day 9 or pre-dose Day 1/Day 10
5. Day 2; clinical chemistry only. Approximately 8 h post-dose. Not Day 11.
6. Day 1 at time points indicated, Day 2, Day 3 and Day 10 (approximately 2 h post-dose only) and Day 12 prior to departure. Not Day 11.
7. ECG on Day 2, not Day 11.
8. Randomisation on Day 1.
9. IMP administration on Day 2 and Day 3, not Day 11 or Day 12.
10. Pre-dose sample on Day 1 should be taken within 60 minutes prior to dose.
11. Pre-dose samples on Day 8, 9 and 10 must be taken within 5 minutes before dose.
12. The 24 h PK sample is taken pre-dose Day 2 or 24 h post last dose on Day 11 within 10 minutes of the of the nominal time for the dosage interval. For details regarding time windows for PK sampling on Days 2, 8, 9 and 10, refer to Section 11.4.1.
13. 48 h after last dose on Day 12. Not Day 3.
14. Day 1 and Day 10 during 24 h in association with PK sampling. Includes sampling for future exploratory analyses of potential GS-248 metabolites.
15. Urine for analysis of AA metabolites and for future analysis of GS-248 metabolites and biomarkers will be collected at the following intervals: 0 to 6 h, 6 to 12 h and 12-24 h post administration of study drug on Day 1 and Day 10. In addition, baseline urine is collected -24 h to -12 h and -12 h to 0 h prior to the first IMP administration on Day -1/Day 1.

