8. Urine for PD analysis will be collected at the following intervals: 0 to 6 h, 6 to 12 h and 12-24 h post administration of celecoxib on Day 1 and Day 10. In addition, baseline urine is collected -24 h to -12 h and -12 h to 0 h prior to the first celecoxib administration on Day -1/Day 1.
9. Breakfast, lunch, snack, dinner and evening snack. Breakfast only on Day 2 and 11.
10. From administration of IMP.

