7.3.1.2 AA metabolites in urine

The AA metabolites that will be analysed in urine are PGEM, PGIM and TXM. The AA metabolite concentration will be normalised by urine creatinine concentration and total excretion over 24 hours will be calculated:

- Actual concentration data
- Values normalised by urine creatinine concentration
 - Formula : $ng/mg = \frac{AA\ metabolite\ (ng/mL) * 1000}{U-creatinine\ (mmol/L) * 113\ (g/mol)}$
- Calculated total excretion over 24 h (described in previous SAP as Normalised values for urine volume)
 - Formula: $ng = AA\ metabolite\ (ng/mL) * urine\ volume\ (ml)$

Each metabolite will be estimated for the absolute and percent change from pre-dose to post-dose. The changes will be presented using summary statistics (one table per variable and comparison) and bar graphs (one graph per variable and comparison). The difference between all treatment groups, see table 3, will be analysed using Wilcoxon Rank Sum test and tabulated.

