7.3.1.3 ADMA, L-Arginine

ADMA/L-arginine and L-arginine will be estimated for the absolute and percent change from pre-dose to 2h, 8h and 24h. The change will be presented using summary statistics (one table per variable and comparison) and bar graphs (one graph per variable and comparison). The difference between all treatment groups, see table 3, will be analysed using Wilcoxon Rank Sum test and will be presented in a table.

7.3.1.4 Renal creatinine clearance 24 h (ClCr):

Formula:

- AeCreatinine (mmol/24h) = Total sum over 24 hours of U-Creatinine (mmol/L) * U-Volume (L), as calculated for each urine fraction and summarized.
 - ClCr (L/h) = AeCreatinine (mmol)*1000 / [24 (h)*P-Creatinine (umol/L)]
 - ClCr (mL/min) = ClCr (L/h) * 1000/60

P-creatinine at day -1 and day 9 will be used for the MAD cohorts in the calculations, for the celecoxib cohort will screening and follow-up values be used.

Renal creatinine clearance will be presented in a table including Wilcoxon rank sum test p-value for the comparison between all the treatment groups.

STATISTICAL ANALYSIS PLAN

Protocol Version No: Final Version 2.0, 29MAY2019

Study Code: GS-1001

CTC Project No: 225-45.2018

CLINICAL TRIAL CONSULTANTS AB

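### Read literally, the SAP's baseline rule takes only the last 12 h urine fraction as baseline for the AA metabolites, and SAP 7.3.1.2 does not say that fractions are summed to 24 h

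*SAP*

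**What the plan says.** SAP 4.3 gives one rule for all variables: "Baseline measurement is defined as the latest measurement prior to first dose of each IMP". The only exception, added in brackets, is for the whole blood assay, whose baseline is set at 24 h before dosing. Urine gets no exception.

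For Part II the protocol (Table 8.1-3 footnote 16, Table 8.1-4 footnote 15) says that "baseline urine is collected -24 h to -12 h and -12 h to 0 h prior to the first IMP administration on Day -1/Day 1". Part IV has the same two fractions (Table 8.1-7 footnote 8): "baseline urine is collected -24 h to -12 h and -12 h to 0 h prior to the first celecoxib administration on Day -1/Day 1". Post-dose urine is divided differently: "0 to 6 h, 6 to 12 h and 12-24 h post administration of study drug on Day 1 and Day 10".

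SAP 7.3.1.2 plans three forms of each metabolite: concentration, a creatinine-normalised value in ng/mg, and "Calculated total excretion over 24 h (described in previous SAP as Normalised values for urine volume"). The formula for the third is concentration times volume, with no sum shown. The contrast is described only in general terms: "Each metabolite will be estimated for the absolute and percent change from pre-dose to post-dose". Table 14.5.1.x then reports absolute and relative change from baseline, each with a Wilcoxon p-value against placebo.

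SAP 7.3.1.4, on creatinine clearance, does state the summation: "Total sum over 24 hours of U-Creatinine (mmol/L) * U-Volume (L), as calculated for each urine fraction and summarized".

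**The concern.** The baseline rule suits point measurements. Urine is an interval measurement, and an amount excreted depends on how long it was collected. Applied as written, the rule selects the -12 to 0 h fraction and leaves out the -24 to -12 h fraction. An amount from 12 h is then set against post-dose amounts that cover 24 h if summed, or 6, 6 and 12 h if not. Since the SAP spells out the sum for creatinine and omits it for the metabolites, a programmer has no instruction that corrects this.

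Urinary PGEM and PGIM are the in-vivo readings of the mechanism in Protocol 6.3: less PGE2, and more prostacyclin through shunting. The size and direction of their changes will be read as evidence on that mechanism. The rule is also better settled in writing now. SAP 3.6 says allocation was withheld until each part's database lock, and SAP section 9 lists the Part II outputs as already delivered, so a choice left open may be made with treatment known.

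**Working it through.** The documents give no expected change in PGEM and no power calculation, so there is no figure of the plan's own to reproduce.

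**Inputs.** Baseline fractions 12 h + 12 h; post-dose fractions 6 + 6 + 12 = 24 h (protocol footnotes above). Let d be the true fall (0 or 50%, for illustration). Let f be the share of 24 h baseline excretion that falls in the -12 to 0 h fraction. The documents do not give f; it is assumed to be 0.5, with a range of 1/3 to 2/3.

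**Excretion, post-dose fractions summed, baseline = last fraction.** Displayed change = (1 - d)/f - 1.

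| f | no effect (d = 0) | true 50% fall |
|---|---|---|
| 1/3 | +200% | +50% |
| 0.4 | +150% | +25% |
| 0.5 | 1/0.5 - 1 = +100% | 0.5/0.5 - 1 = 0% |
| 0.6 | +67% | -17% |
| 2/3 | +50% | -25% |

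With both baseline fractions summed, the displayed change is (1 - d) - 1 = -d: 0% and -50%, whatever f is.

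**Excretion, nothing summed.** At a constant excretion rate, a post-dose fraction of h hours shows (1 - d) x h/12 - 1.

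| fraction | no effect | true 50% fall |
|---|---|---|
| 0-6 h | 6/12 - 1 = -50% | -75% |
| 6-12 h | -50% | -75% |
| 12-24 h | 12/12 - 1 = 0% | -50% |

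**Concentration and ng/mg.** These are not amounts, so collection length does not enter and a 50% fall still shows as about -50%. What remains is day/night variation. Dosing is in the morning, so the 0-6 h and 6-12 h fractions are daytime urine compared with an overnight fraction. The 12-24 h fraction matches it in clock time.

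**Planned rank tests.** On percent change, the literal baseline multiplies each subject's post/pre ratio by 1/f. If f is the same for everyone, ranks and p-values are unchanged. On absolute change the test uses post - f x pre instead of post - pre, and ranks can differ. A simulation shows the size: exact two-sided Wilcoxon test at 5%, 6 active against 6 pooled MAD placebo subjects (3 cohorts x 2), true 50% fall, 4,000 runs. Its assumptions are a between-subject CV of 50%, a within-subject CV of 30% or 50%, and f equal to 0.5 or varying around it with SD 0.08. Power with the 24 h baseline / the 12 h baseline:

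| within-subject CV | f | percent change | absolute change |
|---|---|---|---|
| 30% | constant | 0.674 / 0.674 | 0.456 / 0.710 |
| 30% | SD 0.08 | 0.678 / 0.623 | 0.465 / 0.663 |
| 50% | constant | 0.334 / 0.334 | 0.225 / 0.354 |
| 50% | SD 0.08 | 0.328 / 0.312 | 0.224 / 0.350 |

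On absolute change the mismatched baseline has the higher power here, so lost power is not the complaint. The two readings test different quantities and can give different p-values.

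**The case against.** A reader might infer that the SAP prescribes a 24 h against 12 h comparison, so that a halving of PGEM would be reported as no change. The documents do not support that, for four reasons.

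- **Intent.** A variable named as a 24 h total can have a pre-dose value only if both baseline fractions are added. Protocol 8.1.2 and 8.1.4 describe the baseline collection as lasting 24 h. Protocol 17.1 defines baseline by visit, and both fractions belong to Visit 2.
- **One-sided summation.** The no-change result needs the post-dose fractions summed and the baseline fractions not summed. No text instructs that. It also needs f = 0.5.
- **Scope.** Two of the three forms would still show the fall.
- **Comparison with placebo.** Placebo would shift in the same way, so percent-change contrasts largely survive.

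These are also exploratory endpoints with no stated hypotheses (SAP 3.3), and they may be reported outside the CSR (Protocol 7.3.1). An earlier Part II SAP, which is not among the documents, may define the derivation.

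Most of this stands, and it limits the claim. It does not remove the gap. Evidence of intent shows that the literal rule clashes with the design; it does not tell a programmer to depart from it. The SAP's baseline wording differs from Protocol 17.1, and SAP section 8 does not list the change. SAP section 9 describes the earlier Part II and Part IV plans as superseded. Under the literal baseline the excretion changes are wrong whether post-dose fractions are summed or run singly. The shared placebo offset is not visible in Figure 14.5.3.x, which has one graph per dose group, and it does not preserve the ranks for absolute change.

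**Conclusion.** The point holds as a conflict in the text that should be fixed. SAP 4.3 read literally gives the wrong baseline for interval urine data, and SAP 7.3.1.2 does not correct it.

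The length mismatch is confined to the excretion form. Its size depends on the overnight share, which is assumed, and the per-fraction figures assume a constant excretion rate. The other two forms have a milder problem: two daytime fractions are compared with an overnight one, and half of the baseline collection goes unused.

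Within-group changes, bar graphs and tests on absolute change would be affected. Tests on percent change would be unchanged with a constant share, and lose little power if it varies as assumed. Priority: should fix, since the endpoints are exploratory and the remedy is cheap.

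**What to change.** Add a urine exception to SAP 4.3, and state in SAP 7.3.1.2:

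- Baseline excretion = sum of concentration x volume over -24 to -12 h and -12 to 0 h.
- Post-dose excretion = sum of concentration x volume over 0-6, 6-12 and 12-24 h, separately for Day 1 and Day 10.
- Creatinine-normalised value = summed metabolite amount / summed creatinine amount over the same 24 h.
- Concentration = summed metabolite amount / summed volume over the same 24 h.
- If single fractions are shown, give excretion as a rate (ng/h).

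List the change of baseline definition in SAP section 8. The cost is wording and programming. The fractions are scheduled in both parts, volumes are recorded (Protocol 11.5.2), and urine creatinine is measured to normalise the urine results (Protocol Tables 11.3-1 and 11.3-2).

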4.4 Summary Statistics

In general, all data collected will be presented with summary statistics and given in subject data listings. Summary statistics will include at least number of subjects, mean, standard deviation, median, minimum and maximum for continuous data and frequency and percentage for categorical data. Table with summary statistics will be divided by treatment

STATISTICAL ANALYSIS PLAN

Protocol Version No: Final Version 2.0, 29MAY2019

Study Code: GS-1001

CTC Project No: 225-45.2018

CLINICAL TRIAL CONSULTANTS AB

group and visit where applicable. Subject data listings will be sorted by treatment, dose, subject and timing of assessments.

4.5 Significance Level

All hypothesis testing will use a significance level of 5%.

4.6 Multiple Comparisons/Multiplicity

No adjustment for multiple comparison/multiplicity will be performed, all significant statistical findings, must be reviewed for medical relevance.

4.7 Handling of Dropouts, Missing Data and Outliers

Outliers will be included in summary tables and listings and will not be handled separately in any analyses. No imputation of data will be performed, however a sensitivity analysis will be applied when specific data are missing (applicable for the exploratory endpoints).

Values which are below detection limit will be set to 50% of detection limit.

4.8 Sensitivity analysis

For the exploratory endpoints will a sensitivity approach be performed, i.e. for data which is missing will two set of tables be produced. The first one with all data included and other with data for subjects with complete data.

4.9 Adjustment for Covariates

No adjustments for covariates have or will be performed.

4.10 Examination of Subgroups

No examination of the subgroups has or will be performed.

4.11 Blind Review

Not applicable.

STATISTICAL ANALYSIS PLAN

Protocol Version No: Final Version 2.0, 29MAY2019

Study Code: GS-1001

CTC Project No: 225-45.2018

CLINICAL TRIAL CONSULTANTS AB

5 SUBJECTS

5.1 Subject Disposition

The number of subjects that entered the study, withdrawn subjects, completed subjects and the number of subjects at each visit will be summarised by treatment group.

5.2 Baseline Characteristics and Demographics

The baseline characteristics and demographics have been described in the previous SAP's, GS-1001SAP_v.10_11DEC2019- SAD, GS-1001SAP_v.10_13FEB2020- MAD and GS-1001SAP_v.10_27FEB2020- Part IV. The tables for Part II (MAD) and Part IV (celecoxib) will be combined.

6 TREATMENT INFORMATION AND EXTENT OF EXPOSURE

6.1 Active Treatment

The number of subjects on each IMP will be tabulated using listings and summary statistics.

6.2 Prior and Concomitant Medications

Prior and concomitant medication data have been listed and tabulated by ATC code for each part in the study. It has been specified in previous SAP's. Prior and concomitant medications were coded according to the World Health Organization (WHO) Anatomic Therapeutic Chemical (ATC) classification system.

7 STATISTICAL METHODOLOGY

All parameters will be presented by treatment group and visit using summary statistics. Additional statistical analyses are specified below.

7.1 Primary Endpoint(s) Analysis

Definition of endpoint(s)

The primary endpoints have been described in the previous SAP's, GS-1001SAP_v.10_11DEC2019- SAD, GS-1001SAP_v.1.0_13FEB2020- MAD and GS-1001SAP_v.10_27FEB2020- Part IV. The tables for Part II (MAD) and Part IV (celecoxib) will be combined.

7.2 Secondary Endpoint(s) Analysis

Definition of endpoint(s)

Secondary endpoints have been estimated for Part I (SAD) and Part II (MAD), described in GS-1001_SAP_v.1.0_11DEC2019 - SAD, GS-1001_SAP_v.1.0_13FEB2020 - MAD.

7.3 Tertiary/Exploratory Endpoint(s) Analysis

7.3.1.1 Analysis of mPGES-1 activity (PGE₂ levels) levels using whole blood assay

PGE₂ levels will be estimated for the absolute and percent change from pre-dose to both day 1 and day 10 subsequent timepoints. The change will be presented using summary statistics (one table per variable and comparison) and bar graphs (one graph per variable and comparison). The difference between all treatment groups, see table 3, will be analysed using Wilcoxon Rank Sum test and the p-values will be presented in a separate table (the Wilcoxon Rank sum test will only be applied for the changes between pre-dose and 24h value).

Table 3 – Comparison between treatment groups

Pairwise comparison groups	
Placebo	MAD 20mg
Placebo	MAD 60mg
Placebo	MAD 180mg
Placebo	Celecoxib
Celecoxib	MAD 20mg
Celecoxib	MAD 60mg
Celecoxib	MAD 180mg
MAD 20mg	MAD 60mg
MAD 20mg	MAD 180mg
MAD 60mg	MAD 180mg

STATISTICAL ANALYSIS PLAN

Protocol Version No: Final Version 2.0, 29MAY2019

Study Code: GS-1001

CTC Project No: 225-45.2018

CLINICAL TRIAL CONSULTANTS AB

A bar graph for the absolute and relative changes between pre-dose and Day 1 (24h) including treatment groups from SAD (cohorts 3 to 6 - 5mg, 40mg, 100, mg and 300mg), MAD (20mg, 60mg and 180mg), celecoxib 200 mg BID and Placebo, see table 4, including p-values in comparison to Placebo (using all placebo subjects in one group).

Table 4 – Comparison between treatment groups

Pairwise comparison groups	
Placebo	MAD 20mg
Placebo	MAD 60mg
Placebo	MAD 180mg
Placebo	Celecoxib
Placebo	SAD 5mg
Placebo	SAD 40mg
Placebo	SAD 100mg
Placebo	SAD 300mg
Celecoxib	MAD 20mg
Celecoxib	MAD 60mg
Celecoxib	MAD 180mg
Celecoxib	SAD 5mg
Celecoxib	SAD 40mg
Celecoxib	SAD 100mg
Celecoxib	SAD 300mg
MAD 20mg	MAD 60mg
MAD 20mg	MAD 180mg
MAD 20mg	SAD 5mg
MAD 20mg	SAD 40mg
MAD 20mg	SAD 100mg
MAD 20mg	SAD 300mg
MAD 60mg	MAD 180mg
MAD 60mg	SAD 5mg
MAD 60mg	SAD 40mg
MAD 60mg	SAD 100mg
MAD 60mg	SAD 300mg
SAD 5mg	SAD 40mg
SAD 5mg	SAD 100mg
SAD 5mg	SAD 300mg
SAD 40mg	SAD 100mg
SAD 40mg	SAD 300mg
SAD 100mg	SAD 300mg

A bar graph for Part I (SAD), cohorts 3 to 6 (5mg, 40mg, 100mg and 300mg), the within subject changes between pre-dose and Day 1 (24h) (both absolute and percent) with Wilcoxon test in comparison to placebo will be applied and presented in graphs.

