|---|-------------------|-------------|----------------|-------|-----------|----------------|--------------|-------------|--------|--------|------------------|
| | Visit 1 | Visit 2 | | | | Visit 3 | | Visit 4 | | | Visit 5 |
| Assessment | Day -28 to Day -2 | Day -1 | Day 1 | Day 2 | Day 3 & 4 | Day 5 | Day 6, 7 & 8 | Day 9 | Day 10 | Day 11 | Day 19 (±2 days) |
| Informed Consent | X | | | | | | | | | | |
| Inclusion/exclusion criteria | X | | X ¹ | | | | | | | | |
| Weight/height/BMI | X | | | | | | | | | | X ² |
| Medical/surgical history | X | | | | | | | | | | |
| Demographics | X | | | | | | | | | | |
| HIV, hepatitis B and C | X | | | | | | | | | | |
| Urine Drug Screen ³ | X | X | | | | | | X | | | X |
| Alcohol breath test | X | X | | | | | | X | | | X |
| Pregnancy Test ⁴ | X | X | | | | | | X | | | X |
| Physical Examination | X | | | | | | | | | | X |
| Clinical Laboratory Profile ⁵ | X | | | | | | | | | | X |
| Vital signs | X | | | | | | | | | | X |
| 12-lead paper ECG | X | | | | | | | | | | X |
| Celecoxib administration BID ⁶ | | | X | X | X | X | X | X | X | | |
| Blood sampling for WBA ⁷ | | | X | X | | | | | X | X | |
| Blood sampling for ADMA analysis ⁷ | | | X | X | | | | | X | X | |
| Blood sampling for future biomarker analyses ⁷ | | | X | X | | | | | X | X | |
| Urine collection ⁸ | | X | X | X | | | | | X | X | |
| Meals ⁹ | | X | X | X | | | | X | X | X | |
| Baseline symptoms | X | X | | | | | | | | | |
| AEs and SAEs ¹⁰ | | | | | | | | | | | X |
| Prior and concomitant medications | | | | | | | | | | | X |

1. Confirmation of eligibility prior to randomisation. Day -1 or Day 1.
2. Weight only.
3. Random drug screening test may also be performed at the discretion of the investigator.
4. WOCBP only. Screening: plasma/serum tests, other visits: urine test.
5. Clinical chemistry, haematology, coagulation, urinalysis (dip-stick), see Section 11.3.6.
6. To be taken each morning and evening at the same time (± 1 h). Self-administration at home from the evening of Day 2 to the evening of Day 8.
7. Blood samples for WBA, ADMA and future biomarker analyses are drawn 0 h (within 60 min pre-dose) and 2 h, 8 h and 24 h post administration of celecoxib on Day 1 and Day 10 (24 h samples taken pre-dose on Day 2 and 24 h post last dose on Day 11, respectively).

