8.3 Selection of starting dose and rationale for planned dose escalation

8.3.1 Selection of starting dose in the SAD part

A single oral dose of 1 mg is proposed for the first cohort, since it is estimated that this will yield a pharmacological response close to the Minimum Anticipated Biological Effect Level (MABEL), which corresponds to 20% of the maximum attainable area under the effect (AUE; i.e. inhibition) curve 0-24 h as described in the IB.

In assessment of the pharmacological response in terms of mPGES-1 inhibition, one must consider both the duration and the magnitude of such inhibition, i.e. the AUE. In view of a target human dosing interval of at most 24 h and the projected PK of GS-248, it appears reasonable to apply the AUE from 0 to 24 h [$AUE_{(0-24)}$] as a function of dose in order to define MABEL. In this context, 20% of maximum attainable $AUE_{(0-24)}$ is chosen to constitute MABEL, and is projected to be achieved by a single oral dose of GS-248 between 0.9 and 1.7 mg, based on allometric scaling from dog and cynomolgus monkey, respectively.

The NOAEL in the 28-day dog toxicity study was set at 20 mg/kg, with mean C_{max} and $AUC_{0-24 h}$ values at this dose level of 2500 nmol/L and 23000 h*nmol/L (in males and females combined), respectively. These values set the maximum limits for exposure in humans in this Phase I study.

The predicted exposure at the chosen starting dose in the SAD phase results in exposure margins for C_{max} and $AUC_{0-24 h}$ of 250- and 290-fold, respectively, compared to the exposure at the lowest dose level in the dog study, and 450- and 740-fold, respectively, compared to the

exposure at the NOAEL (Table 8.3-1). All these margins are considered to constitute good safety margins between animals and man. However, it should be realised that the human exposure values used in these calculations are, of necessity, only estimated values.

Table 8.3-1 Exposure margins for mean C_{max} and AUC_{last} values between GS-248-treated animals in the pivotal 28-day toxicity studies and the predicted values in humans in the SAD

| Species | Study No. | Dose level (mg/kg animals) (mg humans) | Duration (days) | Sex | C_{max} (nmol/L) | AUC^a (h*nmol/L) | Exposure margin animals:man ^e (X-fold) | |
|---------|------------|--|--------------------|----------------|-----------------------|------------------------|---|------------------|
| | | | | | | | C_{max} | AUC^a |

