The desired pharmacological effect of GS-248 in humans includes i) blocking the production of PGE₂ via mPGES-1, and ii) increased production of the vasodilatory and platelet-inhibitory PGI₂ via substrate shunting. The latter aspect calls for a pronounced level of inhibition of mPGES-1 over 24 h, to optimise for the desired shunting effect and intravascular PGI₂ synthesis.

A PK/exposure-driven dose escalation strategy will be applied such that the first cohort is expected to yield a systemic exposure corresponding to MABEL and the last cohort will achieve exposures close to the maximum exposure limits, as established by the 28-day dog toxicity study, unless safety or tolerability has previously limited escalation. The escalation steps will be smaller when the maximum exposure limits are approached.

Pharmacokinetics will be evaluated following each cohort and the escalation scheme can be modified based on the totality of acquired PK, safety and tolerability data. In case of signs of unpredictable PK (i.e. highly variable or non-linear PK) escalation steps will be decreased. In case the systemic exposure following the first cohort is appreciably smaller than predicted or below the lower limit of quantification (LLOQ), multiple maximum 8-fold dose escalations will be allowed until the exposure is within the predicted range of the study. If the systemic exposure following the first cohort is appreciably larger than projected, escalation steps will be decreased or, in case of limiting safety or tolerability, de-escalation may be performed. The decision on dose selection will be made by the iSRC, which will have access to all safety, tolerability and PK data (8.3.8).

A tentative dose escalation scheme based on target systemic exposures is shown in Table 8.3-2 where the first and last cohorts are determined by MABEL and maximum exposure limits, and the mid-range of maximum attainable AUE₍₀₋₂₄₎ is expected to be achieved between cohort 2 and 3.

Table 8.3-2 Tentative dose escalation schedule SAD

| Cohort: | 1 | 2 | 3 | 4 | 5 | 6 | (7) |
|--------------------------------------|----------|----------|-----------|-------------|-------------|--------------|-------------|
| Tentative dose (mg) | 1 | 5 | 25 | 75 | 225 | 450 | ≤ 800 |
| Predicted AUC_{0-inf} | 19-31 | 97-150 | 480 – 770 | 1500 – 2300 | 4400 – 6900 | 8700 – 14000 | 16000-25000 |

For details on the prerequisites for the transition from single to multiple dosing, refer to Section 8.3.5.

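### The whole-blood assay is tested only at 24 h and no AUE(0–24) is derived, so with a short half-life the p-value can miss inhibition that lasted most of the day

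*SAP*

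**What the plan says.** SAP 7.3.1.1 summarises PGE₂ as "absolute and percent change from pre-dose to both day 1 and day 10 subsequent timepoints", but for the group comparisons "the Wilcoxon Rank sum test will only be applied for the changes between pre-dose and 24h value". The pairs to be compared are listed in Table 3 (MAD doses, placebo, celecoxib) and Table 4 (the same groups plus SAD cohorts 3 to 6, Day 1).

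WBA blood is drawn pre-dose and at 2, 8 and 24 h: on Day 1 in Part I from cohort 3 (Protocol Table 8.1-2), and on Day 1 and Day 10 in Part II (Table 8.1-4) and Part IV (Table 8.1-7, footnote 7: "2 h, 8 h and 24 h post administration of celecoxib on Day 1 and Day 10").

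Protocol 8.3.1 states that in assessing the response "one must consider both the duration and the magnitude of such inhibition, i.e. the AUE". It applies AUE(0–24) "as a function of dose in order to define MABEL", with 20% of the maximum "projected to be achieved by a single oral dose of GS-248 between 0.9 and 1.7 mg". Protocol 8.3.2 places the mid-range of AUE(0–24) in the escalation, where it "is expected to be achieved between cohort 2 and 3", and says of substrate shunting: "The latter aspect calls for a pronounced level of inhibition of mPGES-1 over 24 h".

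The WBA endpoint (Protocol 7.3.1) and its planned analysis (17.7.1) do not name AUE; 17.7.1 is descriptive only.

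**The concern.** The protocol reasons about response as an area over 24 h, and the samples for a coarse area exist, yet the SAP tests only the last point. That point depends most on half-life. If GS-248 clears quickly, a dose could block mPGES-1 for most of the day and still not separate from placebo at 24 h. The WBA is the one exploratory outcome that the protocol commits to reporting in the CSR, so a non-significant p-value there could be read as absence of effect.

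The restriction is also peculiar to this assay. Urine metabolites are totalled over 24 h (SAP 7.3.1.2), and the Wilcoxon test for ADMA and L-arginine at 2, 8 and 24 h carries no such limit (7.3.1.3). No reason is given for the difference.

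The celecoxib contrasts raise a second question. Celecoxib is given twice daily and GS-248 once daily, so the sample labelled 24 h is not taken at the same time since the last dose.

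**Working it through.** The plan gives no power, effect size or SD for the WBA, so there is no figure of its own to reproduce. The check is an illustration of how far the two measures can part.

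**Inputs from the protocol**
- WBA IC50: 0.4 nM (6.4)
- Predicted Cmax at 1 mg: 4.6–5.6 nmol/L; AUC 19–31 h·nmol/L (Table 8.3-1)
- Predicted half-life (T½): 2–13 h (8.3.8)

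MAD doses of 20, 60 and 180 mg are from SAP 3.4.

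**Assumed, not in the documents:** dose-proportional Cmax reached at 1 h by a linear rise, mono-exponential decline afterwards, no accumulation, and inhibition I = C/(C + 0.4).

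**Formulas**
- C(t) = dose × (4.6 to 5.6) × 2^(−(t−1)/T½) for t ≥ 1 h
- AUE% = (100/24) × ∫I dt over 0–24 h

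**Worked case, 20 mg, T½ 2 h, lower Cmax**
- Cmax = 20 × 4.6 = 92 nM
- C(24) = 92 × 2^(−11.5) = 92 × 0.000345 = 0.0318 nM, so I(24) = 0.0318/0.4318 = 7.4%
- Area over 1–24 h = (2/ln 2) × ln(92.4/0.4318) = 15.48 h
- Area over the first hour = 1 − (0.4/92) × ln(1 + 92/0.4) = 0.98 h
- AUE = 16.46/24 = 69%

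Ranges over Cmax 4.6–5.6 per mg:

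| T½ | Dose | Inhibition at 24 h | AUE(0–24), % of maximum |
|---|---|---|---|
| 2 h | 20 mg | 7–9% | 69–71% |
| 2 h | 60 mg | 19–22% | 80–82% |
| 2 h | 180 mg | 42–47% | 90–91% |
| 3 h | 20 mg | 53–58% | 89–90% |
| 4 h | 20 mg | 81–84% | 95–96% |
| 13 h | 20 mg | 98–99% | 99% |

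At T½ 2 h, 20 mg still shows 99% inhibition at 2 h and 95–96% at 8 h.

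**Which half-life?** Under mono-exponential decline T½ = ln 2 × AUC/Cmax, so the 1 mg predictions give 0.693 × 19/5.6 = 2.4 h to 0.693 × 31/4.6 = 4.7 h. That lies in the lower part of 2–13 h, slightly above the worst case.

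**Check against the protocol's anchor.** At 1 mg and T½ 2 h this model gives an AUE of 34–36%, and more at longer half-lives, not the stated 20%. A variant with decline from time 0, 5.0 nmol/L per mg, and IC50 raised until 1 mg gives 20% yields for 20 mg:
- T½ 2 h: 2% at 24 h, AUE 53%
- T½ 3 h: 14%, AUE 65%
- T½ 4 h: 30%, AUE 72%
- T½ 13 h: 72%, AUE 82%

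So the choice of IC50 matters as much as the half-life.

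**What this does to the test.** With 6 against 6 (three MAD cohorts × 2 placebo = 6), the smallest two-sided exact p is 2/924 = 0.0022, so group size does not rule out significance. Simulated power of the 24 h test against placebo used decline from time 0, both IC50 choices, independent errors and an assumed SD of 20–30 percentage points per sample:

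| T½ | 20 mg | 60 mg | 180 mg |
|---|---|---|---|
| 2 h | 4–7% | 5–19% | 12–72% |
| 3 h | 9–95% | 34–100% | 80–100% |

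A test on the trapezoid AUE has at least 99% in every case.

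**The area available from the samples.** On Day 1, with zero inhibition at time 0, the trapezoid weights the 2, 8 and 24 h values by 4/24, 11/24 and 8/24. For the worked case: (4 × 99.4 + 11 × 95.3 + 8 × 7.4)/24 = 63%, against the true 69%.

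**Celecoxib timing.** The Day 2 sample is pre-dose, about 12 h after the evening celecoxib dose but 24 h after GS-248. For Day 11, footnote 7 of Table 8.1-7 says 24 h after the last dose, while dosing on Day 10 is morning and evening and Protocol 8.1.4 times the urine from the last morning dose. These passages do not agree.

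**The case against.** A reader might infer that the SAP departs from a prescribed endpoint. The documents do not support that: the AUE sentence is worded generally, but it stands in the starting-dose section and serves to define MABEL. Neither Protocol 7.3.1 nor 17.7.1 asks for AUE.

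A reader might also infer that an active dose will look inactive. Only the p-value is at risk. The 2 h and 8 h changes are tabulated, and the shells go further than the text: Figures 14.4.3.x and 14.4.6.x show p-values with all time points, and Tables 14.4.1.1 and 14.4.4.1 carry Wilcoxon rows by assessment time point. That conflict is a firm defect in its own right.

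The 24 h value is not a poor choice in itself. With once-daily dosing and an aim of inhibition sustained over 24 h, a trough test asks a relevant question, and a null result there is informative. AUE could rate highly a dose that has worn off. This stands, and it is why replacing the 24 h test is not warranted.

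Finally, it is tempting to say that the comparison is tilted towards celecoxib. Time since dose does differ on Day 2, but both samples are troughs of their own regimens, and the Day 11 timing is unresolved. AUE would not settle it: no sample lies between 8 and 24 h, so the effect of the evening celecoxib dose is not captured.

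**Conclusion.** The point holds in a limited form. Under the SAP text the WBA is tested at 24 h only, and no AUE(0–24) is derived although the protocol's own reasoning uses it and the samples exist. At a half-life near 2 h the gap is large (20 mg: 7–9% at 24 h against AUE 69–71%). With IC50 0.4 nM it narrows quickly, to 53–58% against 89–90% at 3 h, and closes by 13 h. With IC50 fitted to the 20% anchor it persists longer. The problem is therefore plausible and not certain. It rests on an assumed concentration–effect model, and the power figures also on an assumed SD. The documents reviewed give no observed half-life.

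The consequence is modest: the endpoint is exploratory, SAP 3.3 states no hypotheses, and SAP 4.6 makes no multiplicity adjustment.

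**What to change.** In SAP 7.3.1.1:

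1. Add per-subject AUE(0–24) of percent inhibition from pre-dose, by trapezoid on the 0, 2, 8 and 24 h samples, for Day 1 and Day 10. Make it a second pre-specified tested summary for the Table 3 contrasts, and on Day 1 for the Table 4 contrasts. State which assay variable it uses (the shells list WBA-DMSO, WBA-MF63 and mPGES-1 activity) and the rule when a sample is missing. State also that Day 10 is referred to the pre-first-dose baseline. SAP 4.3 defines the WBA baseline as 24 h pre-dose while the protocol samples within 60 minutes before dosing; reconcile these.
2. Keep the 24 h test and label it a trough comparison.
3. Reconcile the 24 h-only sentence with the shells that show p-values at all time points.
4. For celecoxib contrasts, report that the Day 2 sample is about 12 h after the last celecoxib dose and 24 h after GS-248, and reconcile the Day 11 timing in Protocol 8.1.4 and Table 8.1-7.

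**Cost:** wording and one derived variable, with no new samples. It adds one more set of unadjusted exploratory p-values: 32 pairs on Day 1 (Table 4, which includes the 10 of Table 3) plus 10 on Day 10, so 42. The area is coarse, and it does not fully even out the celecoxib comparison.
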